### **Category Fluency**

This is a widely used measure of verbal fluency. The participant is asked to name different exemplars of a given semantic category (e.g., animals), and the number of unique exemplars named is scored[51].

### **Trail Making Tests (A and B)**

These are tests of processing speed and executive function. Both Parts A and B depend on visuomotor and perceptual-scanning skills. Part B also requires cognitive flexibility in shifting from number to letter sets under time pressure. The participant's performance is judged in terms of time[52].

### **The Multilingual Naming Test (MINT)**

The MINT is a language test that examines one's ability for visual object naming [48, 69]. Line drawings are presented to the participant with the instruction to say the name of the object.

### **Phonemic Fluency**

This is a widely used measure of word generation that may be sensitive to dysfunction in the dominant frontal lobe [51]. In this version, the participant is asked to say as many words as possible that begin with the letter "F" in 60 seconds, and then as many words that begin with the letter "L" in 60 seconds.

### **Word Reading**

This is a test of word reading that includes regularly spelled and irregularly spelled words. The participant is asked to read out loud from the regular and irregularly spelled word lists. Accurate word reading is scored.

### **Semantic Associates Test**

This is a test of knowledge of the meaning of objects [53]. In this test, a participant reviews pairs of pictures and is instructed to select those that depict related objects. Correct associations are scored.

### **Semantic Word Picture Matching**

This test evaluates spoken word recognition and assesses for semantic errors in word comprehension. The stimuli consist of four-picture displays including pictures of four objects that are semantically related. One of the objects is named by the examiner and the participant is asked to point to that object.

### **Northwestern Anagram**

This is a test of grammatical knowledge[54]. In this test, the participant is shown pictures and is then asked to assemble a sentence describing the pictures using printed words that are provided.

### **Sentence Repetition**

This is a test of oral repetition of sentence-length utterances. A sentence is read out loud to the participant. The participant then repeats the sentence verbatim. Correct sentences, omitted words and semantic errors are recorded for scoring purposes.

### **Noun and Verb Naming**

This is a test of confrontation naming of objects and actions. In this test, the participant is shown pictures of objects or things, as well as pictures of people doing various actions. The participant is then asked to name each picture as quickly and as accurately as possible. The primary measure of performance is the noun-to-verb ratio[55].

### ***Sentence Reading***

In this test, the participant is given a sheet of paper with five short sentences and is asked to read the sentences out loud. The primary measure of performance is the number of accurately read sentences.

#### **7.3.2 Additional Cognitive Tests:**

##### ***Alzheimer's Disease Assessment Scale-Cognitive (ADAS-Cog13)***

The ADAS-Cog13 [56] is an in-person examiner-administered, structured scale that evaluates memory, reasoning, language, orientation, ideational praxis and constructional praxis. Ratings of spoken language, language comprehension, word finding difficulty, and ability to remember test instructions are also obtained.

##### ***Digit Symbol Substitution Test***

The Digit Symbol Substitution test [57] measures complex attention. The numbers 1-9 are paired with different nonsense symbols. A string of these numbers is randomly printed directly above a row of blank squares. Following a short series of practice trials, the participant must use the key to fill in the blank squares with the correct nonsense symbol in order working from left to right across the rows. This test engages multiple cognitive abilities including attention, psychomotor speed, complex scanning, visual tracking, and immediate memory.

##### ***Mini-Mental State Examinations (MMSE)***

The MMSE is a brief, frequently used screening instrument for Alzheimer's disease drug studies [58]. The MMSE scale evaluates orientation, memory, attention, concentration, naming, repetition, comprehension, and ability to create a sentence and to copy two overlapping pentagons. The MMSE will only be administered once during the screening visit.

Note: The MMSE cannot be administered on the same day as the MoCA. MMSE should be done at the screening visit. MoCA should be administered at a subsequent visit.

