## 3.0 SCIENTIFIC AIMS

### 3.1 Aim 1

To compare the baseline and longitudinal cognitive and functional characteristics of EOAD compared to LOAD and identify optimal outcome measures for clinical trials.

**H1a:** Controlling for performance on episodic memory tests, EOAD will show greater impairment in executive, language and visuospatial function compared to ADNI LOAD.

**H1b:** EOAD will show more rapid decline on MMSE, ADAS-Cog and CDR-SB compared to ADNI LOAD.

**H1c:** A data-driven analysis of functional ratings and psychometric test scores will identify measures more sensitive to change over time in the full spectrum of EOAD (amnestic and non-amnestic subtypes) than existing composite measures (ADAS-Cog and CDR-SB), leading to a new EOAD composite outcome measure for use in future clinical trials and observational studies.

**Rationale for Aim 1:** Multiple small studies have demonstrated greater impairment in non-memory compared to memory performance[5-7] and more rapid cognitive decline in EOAD than in LOAD[8, 9]. Among these studies the study sample composition (e.g. inclusion of autosomal dominant or focal variants like lvPPA/PCA), assessment and outcome measures vary. Whether clinical trial outcomes employed in LOAD trials (emphasizing episodic memory) should be applied to EOAD or be modified to account for the predominant non-amnestic deficits remains a critical, unanswered question. In this aim we will test both traditional and novel cognitive and functional outcome measures in the full EOAD spectrum defined by current NIA-AA criteria. Our ultimate goal is to empirically reduce our broader battery into a short battery of measures that are especially sensitive in EOAD and feasible for clinical trials.

### 3.2 Aim 2

To compare baseline and longitudinal MRI, amyloid PET, tau PET and CSF and plasma ATN measures between EOAD and LOAD and identify optimal outcome measures for clinical trials.

**H2a:** EOAD will show greater baseline and longitudinal changes in cortical gray matter atrophy and tau burden than matched ADNI LOAD participants, but no differences in baseline or longitudinal amyloid PET, plasma or CSF measures.

**H2b:** Baseline and longitudinal change in cortical tau, gray matter atrophy, CSF and plasma measures will correlate with baseline and longitudinal measures of cognitive function.

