## **7.3 Cognitive Testing**

### **7.3.1 NACC Uniform Data Set (UDS) and Frontotemporal Lobar Degeneration (FTLD) Neuropsychological Batteries**

#### ***Montreal Cognitive Assessment (MoCA)***

The MoCA is a rapid screening instrument designed to help health professionals detect cognitive dysfunction. It assesses numerous cognitive domains: attention and concentration, executive function, memory, language, visuospatial skills, conceptual thinking, calculations and orientation[47].

Note: The MoCA cannot be administered on the same day as the MMSE. MMSE should be done at the screening visit. MoCA should be administered at a subsequent visit.

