#### **Boston Naming Test**

The Boston Naming Test may be used in place of the MINT in order to administer in different languages. The Boston Naming Test is a measure of the ability to orally label (name) line drawings of objects. This test is sensitive to aphasia and also to object recognition deficits.

Results from the NACC Uniform Data Set Neuropsychological Battery Crosswalk Study will be used to allow scores to be converted to equivalent scores on the Craft Stories and MINT tests, respectively [69].

A summary of the neuropsychological testing may be entered in a participant's medical record for clinical purposes.

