#### ***7.4.2.6 Flortaucipir***

Cognitively impaired and CN participants will undergo a flortaucipir PET as outlined in Appendix 1. Participants from select international sites will not complete Tau PET scans. The site study physicians will evaluate each participant prior to administration of flortaucipir to determine if they are still suitable to undergo the scan (e.g., previous research PET scan exposure in the previous 12 months). For women of childbearing potential, a urine pregnancy test will be obtained and negative result confirmed on the day of scanning.

Baseline tau PET results for all newly recruited cognitively impaired participants, positive and negative, will be provided to sites. Participants from select international sites will not complete tau PET scans and therefore will not receive tau PET results. For sites with participants past their baseline timepoint at the time when protocol version 8.0 was implemented, tau PET scan results related to their next study visit timepoint will be provided. The Site PI or an affiliated study physician will be responsible for disclosing the results to the study participant and their family. The clinician should follow best practices in disclosing tau PET results. At Baseline, tau PET scan results and amyloid PET scan results should be disclosed at the same time. If this is not possible due to scheduling conflicts, the study clinician will provide amyloid PET scan results prior to disclosing tau PET scan results. Whenever feasible, results should be disclosed in person. If an in-person disclosure is not feasible due to geographic distance or other factors, a telemedicine appointment could be considered a viable substitute. Disclosure of results by phone call only is

discouraged but allowable at the discretion of the Site PI.

Longitudinal tau PET scans for the EOAD and EOnonAD cohorts will not receive an official read, however trans-axial images may be provided to the participant at the discretion of the site PI.

Tau PET scans from the CN cohort will not receive an official read and results will not be disclosed.

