#### **Aim 1**

We will have 90% power to identify a -0.26 group difference in mean composite cognitive Z-scores between EOAD and LOAD participants after controlling for episodic memory performance. We will have 90% power to detect an average difference of 0.7 in decline in CDR-SB between EOAD and ADNI LOAD.

Similarly, we will have 90% power to identify an effect size of -1.5 for decline in MMSE.

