
a) Visit procedures may be split over multiple days without constituting a protocol deviation.
 
b) Timing for result disclosure is not set and dependent on the availability of the genetic screening results.
 
c) Post mortem brain donation discussion to confirm consent/interest. If participant refuses to participate, no further inquiry should take place. Undecided participants will be approached at each study visit until they consent or refuse to participate.
 
d) The NACC UDS and FTLD modules include demographics, clinical, cognitive, functional, and behavioral assessments.
 
 
• Version C2 the NACC UDS Neuropsychological Battery will be used in this study
 
• UDS forms A1, A3, A5, B4-B9, C2, D1, and D2 are required for LEADS
 
• UDS forms A5/D2, D1a, and D1b will take the place of A5, D2, and D1 if using UDSv4
 
• FTLD forms B3F, B9F, C1F-C6F, E2F, and E3F are required for LEADS
 
 
e) The MMSE and MoCA cannot be administered on the same day. MMSE is required at screening to confirm CN eligibility. MMSE can be done anytime between screening and baseline for CI participants.
 
f) Can be conducted anytime between screening and baseline for CI participants if sufficient testing has been completed to meet NIA-AA criteria for MCI due to AD or probable AD. These activities must occur at Screening for CN participants.
 
g) If a female is not surgically sterile or post-menopausal by two years, a pregnancy test will be performed prior to amyloid, tau, and FDG PET. Only participants with a negative result will be eligible for PET scanning.
 
h) The first MRI scan should be done at screening unless a previously existing MRI within 12 months can be used to assess overall eligibility and safety prior to LP procedure. If a previous scan is not available, the study MRI must be completed at the Screening Visit to facilitate eligibility determination. A study MRI must be completed within the 60 day visit window regardless of a pre-existing MRI being used to assess study eligibility. See section 7.6.4 for more detail.
 
i) All attempts should be made to acquire the full 60 minute MRI protocol; however the MPRAGE and 3D FLAIR should be prioritized. The MPRAGE and 3D FLAIR are the mandatory sequences for enrollment. If needed, the other sequences may be skipped for any reason without constituting a protocol deviation. Note the reason for non-completion in the source documents.
 
j) The amyloid and tau PET scans can be conducted anytime between screening and baseline following MRI. Inclusion/exclusion must be confirmed prior to both scans. The amyloid and tau PET scans must be conducted at least 12 hours apart.
 
k) At the Screening Visit, EOAD and EOnonAD participants will view a video that will discuss the implications of mutations in known ADAD loci. The participant will also be asked if they would like to speak with a genetic counselor to verify their understanding of the implications of genetic testing and answer any questions the participant may have. These participants at international sites may meet with a genetic counselor or investigator with appropriate clinical training in genetic counseling as opposed to watching the video. Written informed consent will be obtained on all participants prior to genetic testing (see section 7.2 Genetic Counseling and Testing section for more detail). Disclosure will be performed as outlined in section 7.1.6.
 
l) Amyloid and tau disclosure is required for EOAD and EOnonAD participants only and should be conducted between screening and baseline. Amyloid disclosure should be conducted within the 60 day visit window. Tau disclosure may be conducted outside of the 60 day visit window due to the timing of the scan and availability of the PET read. FDG PET disclosure is required for EOnonAD participants only. FDG disclosure may be conducted outside of the 60 day visit window due to the timing of the scan and availability of the PET read.
 
m) The FDG PET scan at Baseline applies to CN and EOnonAD participants only. EOAD participants do not receive an FDG PET scan. The FDG PET scan for EOnonAD participants cannot be scheduled until after amyloid disclosure. For sites that have radiation safety committees (RSC), ability to conduct FDG PET scans will also be contingent on local RSC approval.
 
n) To be completed within 48 hours of lumbar puncture. Additionally, a telephone call will be made within two weeks post amyloid results disclosure. See section 7.1.4 for more detail.
 
o) May be provided to participants at the discretion of the PI. See section 7.1.8 for more detail.
 
p) Blood for genetic testing will be drawn for EOAD and EOnonAD participants only; CN participants will not have blood drawn for genetic testing.
 
q) PBMC samples must be collected and shipped the same day. Fasting is not required. PBMC sample collection is optional for international sites. If collected, international sites will store PBMC samples locally. See NCRAD Biospecimen, Collection, and Shipping manual for more details.
 
r) LP should be collected after a minimum 6-hour fast (preferably in the morning after an overnight fast). FDG-PET should be collected after an overnight fast for scans conducted in the morning, or a minimum 4-hour fast for scans collected later in the day; prior to the scan, a blood glucose measurement will be made by finger stick and scans will be postponed or rescheduled if the reading is > 180 mg/dL.
 
s) Can be conducted anytime between screening and baseline. Completion of safety lab report and MRI review with PI signature are required prior to LP. See section 7.6.2 for more detail.
			

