## EOAD Participants – Longitudinal Visits

Procedure	Visit	Genetics Status Disclosure	Month 12 a	Month 24 a	Month 36 a	Month 48 / Ongoing Annual Visits a	Annual Neuropath. Phone Check c	Early Termination d
Window Period (days)	See footnote e					+/- 60 b		
Brain donation discussion/provisional consent c,r			X	X	X	X	X	X
Vital Signs			X	X	X	X		X
Neurological and Physical Exams			X	X	X	X		X
Demographics & Medical History r			X	X	X	X		X
Clinical Diagnosis and Clinical Symptom Assessment			X	X	X	X		X
Sex and Reproductive Health Questionnaire r					X o			
Area Deprivation Index Score r					X o			
Concomitant Medications r			X	X	X	X		X
NACC UDS and FTLD Modules, and Neuropsychological Battery f,r			X	X	X	X		X
Amsterdam IADL Questionnaire r			X	X	X	X		X
ADAS-Cog13 r			X	X	X	X		X
Rey Auditory Verbal Learning Test (RAVLT) r			X	X	X	X		X
TabCat: Flanker, Line Length, Line Orientation, and Match			X	X	X	X		X
CDR r			X	X	X	X		X
Pregnancy Test g			X	X	X			
3T MRI/fMRI h			X	X	X			X
Amyloid PET Scan i			X	X	X			
Tau PET Scan i,p,q			X	X	X			
Adverse Event r			X	X	X	X		X
Tau Status Disclosure p,q,r					X p			
Genetic Counseling r,s,t	X							
Study Participation Report j			X	X	X	X		X
Blood for AD blood biomarkers m , DNA, and RNA, PBMC k			X	X	X	X		X
LP Safety Labs (CBC, coagulation profile)			X	X	X			X
Lumbar Puncture (optional) l,m			X	X	X			X
Wellness Check n,r			X	X	X			X

- a) Visit procedures may be split over multiple days without constituting a protocol deviation.
- b) Longitudinal visits should commence within 365 days **+/- 60 days** from the previous visit. However, there must be at least 365 days between the first PET scan of the previous visit and the first PET scan of the next yearly visit. There must also be at least 365 days from second-to-second PET, so that there are no more than two PET scans in a year. FDG PET is not subject to this consideration; it can be the third PET in 365 days. Every attempt should be made to complete longitudinal visits within 60 days.

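### MMSE decline is hypothesised and given 90% power, but the MMSE is scheduled only once, so no MMSE change can be estimated in LEADS participants

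*Protocol*

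**What the plan says.** Section 3.1 (Aim 1) states H1b as: "EOAD will show more rapid decline on MMSE, ADAS-Cog and CDR-SB compared to ADNI LOAD". Section 21.1.4, under Aim 1, supports two decline comparisons with power. One is a difference of 0.7 in CDR-SB decline. For the other it says: "Similarly, we will have 90% power to identify an effect size of -1.5 for decline in MMSE". Section 21.1.2 assigns longitudinal cognitive change to linear mixed models and machine learning.

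The assessment text differs. Section 7.3.2 says of the test: "The MMSE will only be administered once during the screening visit". Footnote e to the screening and baseline table in Appendix 1 relaxes only the timing for the impaired cohorts: "MMSE can be done anytime between screening and baseline for CI participants". The three longitudinal tables (EOAD, EOnonAD, CN) have no MMSE row.

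The global screen that recurs is the MoCA. Section 7.3.1 lists it within the NACC UDS battery, and Appendix 1 repeats that battery at each annual EOAD visit. The two screens are kept apart: "The MoCA cannot be administered on the same day as the MMSE".

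**The concern.** Decline is a within-person quantity and needs at least two scores per person on the same measure. The hypothesis and the power statement assume a repeated MMSE in the EOAD cohort; the procedures and the schedule provide one. Within Aim 1 only two decline measures carry a power figure, and one of the two has no scheduled data behind it. A reader relying on section 21.1.4 would believe that the study can deliver a comparison of MMSE decline when it cannot. The gap also becomes harder to close with time, because visits already completed hold no scheduled MMSE.

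**Working it through.** **1. Count of scheduled occasions, EOAD, from Appendix 1**

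| Measure | Screening/Baseline | M12 | M24 | M36 | M48/ongoing | Total to M48 |
|---|---|---|---|---|---|---|
| MMSE | 1 | 0 | 0 | 0 | 0 | 1 |
| ADAS-Cog13 | 1 | 1 | 1 | 1 | 1 | 5 |
| CDR | 1 | 1 | 1 | 1 | 1 | 5 |

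The early termination visit adds 1 for ADAS-Cog13, 1 for CDR and 0 for MMSE. Footnote e moves the single MMSE within the screening-to-baseline window; it does not add a second one.

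**2. Consequence for estimation**

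Change scores available per participant = occasions - 1. For the MMSE this is 1 - 1 = 0; for ADAS-Cog13 and CDR it is 5 - 1 = 4. In a linear mixed model with time since baseline, every EOAD MMSE value sits at or before time zero. The EOAD slope, and with it the difference in slope from LOAD, is therefore not estimable. This does not depend on N.

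- H1b measures with scheduled repeat data: 2 of 3.
- Aim 1 decline power statements with scheduled repeat data behind them: 1 of 2 (CDR-SB has it, MMSE does not).

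**3. Attempt to reproduce the stated 90%**

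This cannot be done. The protocol gives no SD of MMSE change, no LOAD sample size for the calculation and no time span, and it does not say whether -1.5 is in points or standardised. The same inputs are missing for the CDR-SB figure of 0.7, so the count above shows only that CDR-SB has repeat data, not that its power is right.

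**4. Illustration: would sample size be the obstacle if the MMSE were repeated?**

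Inputs: alpha 0.05, assumed two-sided because the protocol does not state it; power 90%; 650 EOAD (section 21.1.4). The LOAD sizes and SDs below are assumptions; section 1.0 says only that ADNI has up to 2000 LOAD participants. The sum of the two normal quantiles is 3.2415.

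*Read as 1.5 points.* The SD of change at which power is exactly 90% is SD = 1.5 / (3.2415 × √(1/650 + 1/n_LOAD)).

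- n_LOAD = 200: 1.5 / (3.2415 × 0.0809) = 5.72 points
- n_LOAD = 650: 1.5 / (3.2415 × 0.0555) = 8.34 points
- n_LOAD = 2000: 1.5 / (3.2415 × 0.0451) = 10.25 points

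Conversely, n per group = 2 × (3.2415 × SD / 1.5)², rounded up: 85 for an SD of 3, 234 for an SD of 5, and 598 for an SD of 8.

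*Read as a standardised effect.* n per group = 2 × (3.2415 / 1.5)² = 9.3, so 10.

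Under these assumptions 650 EOAD would be enough in most readings. What is missing is the second measurement, not participants.

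**5. Could another provision supply MMSE change?**

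- *The annual battery.* Section 7.3.1 describes the MoCA and not the MMSE; the MMSE is described separately in 7.3.2.
- *A conversion.* The only crosswalk the protocol names is in section 7.3.3. It takes substitute tests at international sites and "will be used to allow scores to be converted to equivalent scores on the Craft Stories and MINT tests". No MoCA-to-MMSE conversion is stated.

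**The case against.** The strongest objection is one of weight. LEADS is a natural history study without a single primary endpoint. The primary objectives and the Aim 1 analysis text do not name the MMSE, and H1c uses ADAS-Cog and CDR-SB as the existing measures to improve on. MMSE decline is one of three measures in one of 16 lettered hypotheses, and no participant is put at risk. Giving the MMSE once beside an annual MoCA is also a defensible choice in itself. All of this stands, and it limits the reach of the point: H1b as a whole and Aim 1 do not fail.

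A second objection is that MMSE scores may reach the study by other routes. Section 7.0 allows data to be shared from co-enrolled studies and lets international sites contribute existing clinical assessments; section 8.1 allows one re-screen. This is why the conclusion is confined to scheduled data. It does not rescue the power figure. Nothing says those sources hold serial MMSE scores, international sites contribute only about 40 impaired participants, and a re-screen falls before follow-up.

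A third is that an analysis plan might deal with it. An analysis plan can choose a model or a conversion, but it cannot create follow-up scores that the schedule does not collect.

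**Conclusion.** The point holds. The MMSE component of H1b cannot be tested from scheduled LEADS data, and the 90% power for MMSE decline describes a property the design does not have, at 650 EOAD participants or any other number. The prose in section 7.3.2 and all the Appendix 1 tables agree, so a table lost in extraction does not explain it. The size is 0 scheduled MMSE change scores per participant, 1 of 3 H1b measures lost, and 1 of 2 Aim 1 decline power statements without data. The conclusion rests only on the count of scheduled administrations; the sample size illustrations rest on assumed SDs and LOAD numbers and are not needed for it. The ADAS-Cog and CDR-SB parts of H1b are unaffected. Aim 2 separately powers an annualised imaging change. Nothing ties the 650 to the MMSE figure. The correction should be made because the text claims a power that the schedule rules out.

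**What to change.** **Preferred: change the text.** Remove MMSE from the decline measures in H1b and delete the -1.5 sentence in section 21.1.4. Keep ADAS-Cog and CDR-SB as the H1b decline outcomes with no new ranking between them, and keep the MMSE for baseline description and CN eligibility. This costs one named decline outcome and needs no new visits or participants. If a global screen is still wanted in H1b, the MoCA from the annual battery could be named, provided that repeated MoCA data exist in the ADNI LOAD comparator, which this protocol does not show. The MoCA would need its own power statement if power is to be claimed.

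**Alternative: collect the data.** Add the MMSE to the EOAD longitudinal table on a different day from the MoCA. Footnote a to that table already allows this: "Visit procedures may be split over multiple days without constituting a protocol deviation". The cost is one more test at each annual visit and the burden of the separate day. Completed visits stay without a scheduled MMSE, and section 7.4.2.6 shows that such visits may exist: "For sites with participants past their baseline timepoint at the time when protocol version 8.0 was implemented".

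**Alternative: specify a conversion.** If MMSE equivalents are to be derived from the annual MoCA, name the conversion and restate the power with the conversion error included.

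If an MMSE power sentence is kept under either alternative, it should give the unit, the time span, the SD of change and the LOAD sample size.
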